6.4.5 Bath Ankylosing Spondylitis Functional Index (BASFI)

The BASFI is a set of 10 questions designed to determine the degree of functional limitation in those patients with AS. The ten questions were chosen with major input from patients with AS. The first 8 questions consider activities related to functional anatomy. The final 2 questions assess the patients' ability to cope with everyday life. A 0 through 10 scale (captured by a continuous VAS) is used to answer the questions. The mean of the ten scales gives the BASFI score – a value between 0 and 10.

6.4.6 Bath Ankylosing Spondylitis Disease Activity Index (BASDAI)

The BASDAI consists of a 0 through 10 scale (0 being no problem and 10 being the worst problem, captured as a continuous VAS), which is used to answer 6 questions pertaining to the 5 major symptoms of AS:

- 1. Fatigue
- 2. Spinal pain
- 3. Joint pain / swelling
- 4. Areas of localized tenderness (called enthesitis, or inflammation of tendons and ligaments)
- 5. Morning stiffness duration
- 6. Morning stiffness severity

To give each symptom equal weighting, the mean (average) of the two scores relating to morning stiffness is taken (questions 5 and 6). The resulting 0 to 10 score is added to the scores from questions 1-4. The resulting 0 to 50 score is divided by 5 to give a final 0–10 BASDAI score. Scores of 4 or greater suggest suboptimal control of disease, and patients with scores of 4 or greater are usually good candidates for either a change in their medical therapy or for enrollment in clinical trials evaluating new drug therapies directed at AS. BASDAI is a quick and simple index taking between 30 seconds and 2 minutes to complete.

6.4.7 Bath Ankylosing Spondylitis Metrology Index (BASMI linear)

The BASMI is a validated instrument that uses the minimum number of clinically appropriate measurements that assess accurately axial status, with the goal to define clinically significant changes in spinal movement. Parameters include:

- 1. Lateral spinal flexion
- 2. Tragus-to-wall distance
- 3. Lumbar flexion (modified Schober)
- 4. Maximal intermalleolar distance
- 5. Cervical rotation angle

Additionally, the following assessments should be taken:

- 6. Chest expansion
- 7. Occiput-to-wall distance

Detailed information on the assessments is described in Appendix 4.

6.4.8 Medical Outcome Short Form Health Survey (SF-36) Version 2 (Acute Form)

The SF-36 is a widely used and extensively studied instrument to measure health-related quality of life among healthy patients and patients with acute and chronic conditions. It consists of eight subscales that can be scored individually: Physical Functioning, Role-Physical, Bodily Pain, General Health, Vitality, Social Functioning, Role-Emotional, and Mental Health (Ware 1993). Two overall summary scores, the Physical Component Summary (PCS) and the Mental Component Summary (MCS) also can be computed (Ware 1994). The SF-36 has proven useful in monitoring general and specific populations, comparing the relative burden of different disease, differentiating the health benefits produced by different treatments, and in screening individual patients.

The purpose of the SF-36 in this study is to assess the health-related QoL of patients. Given the acute nature of this disease, version 2, with a 1-week recall period, will be used in this study. Investigator must review the results timely and document adverse events, if applicable.

6.4.9 ASAS Health Index

The ASAS Health Index (ASAS HI) is an index that measures an individual's status of functioning, disability and health in individuals and is designed specifically for spondyloarthritis patients. (ASAS HI) (12).

The ASAS HI is a linear composite measure that contains 17 items of functioning and health and 9 environmental factors addressing categories of support/relationships, attitudes and health services with dichotomous response options: "I agree" and "I do not agree". The result forms a unidimensional scale providing a sum score representing a wide spectrum of different levels of functioning (Kiltz et al. 2014).

6.4.10 High sensitivity C-reactive protein (hsCRP)

This assessment will be performed in order to identify the presence of inflammation, to determine its severity, and to monitor response to treatment.

Since the results of this test may unblind study personnel, results from the central laboratory will be provided for Screening and baseline only. The hsCRP results from samples collected during the treatment period will be revealed following database lock only.

Novartis Confidential Page 45
Amended Protocol Version v01 Clean Protocol No. CAIN457FDE03

6.4.11 Erythrocyte sedimentation rate (ESR)

ESR is helpful in diagnosing inflammatory diseases and is used to monitor disease activity and response to therapy. ESR will be performed locally at the investigative site using a centrally provided assessment kit.

6.4.12 Appropriateness of efficacy assessments

The ASAS-NSAID score is used to determine the NSAID sparing effect of biologic i.e. the timing of discontinuation/tapering of NSAID(s) after initiating treatment with Secukinumab.

The other efficacy outcome measures used in this study are the standard measures used across all AS trials.

6.5 Safety

- QuantiFERON TB-Gold test or PPD skin test
- Chest X-ray or MRI
- Physical examination
- Vital signs
- Height and weight
- Laboratory evaluations
- Pregnancy and assessment of fertility
- Local tolerability (injection site reactions)
- Tolerability of Secukinumab

All blood draws and safety assessments should be done prior to study treatment administration. Appropriate safety assessments (e.g. evaluation of AEs and SAEs including injection site reactions) should be repeated after the dose is administered.

6.5.1 QuantiFERON TB-Gold test or PPD skin test

Either a QuantiFERON TB-Gold test **or** a PPD skin test must be performed at Screening. Patients with a positive test may participate in the study if further work up (according to local practice/guidelines) establishes conclusively that the patient has no evidence of active tuberculosis, or if presence of latent tuberculosis is established then treatment according to local country guidelines must have been initiated.

QuantiFERON TB-Gold test

- A QuantiFERON TB-Gold test is to be performed at the second Screening visit and the results to be known prior to randomization to determine the patient's eligibility for the trial. The test will be used to screen the patient population for latent tuberculosis infection.
- The test will be analyzed by the central laboratory. Details on the collection, processing and shipment of samples and reporting of results by the central laboratory are provided in the laboratory manual.

PPD skin test

• A PPD skin test is to be performed at Screening and read before randomization to determine the patient's eligibility for the trial. The test dose is bioequivalent to 5 tuberculin units of

standard PPD injected intradermally, usually into the volar surface of the forearm. The site is cleaned and the PPD extract is then injected into the most superficial layer under the skin. If given correctly, the injection should raise a small wheal of about 5 mm, which resolves within 10-15 minutes.

Because the reaction (induration) will take 48-72 hours to develop, the patients must return to the study center within that time for a proper evaluation of the injection site. This will determine whether the patient has had a significant reaction to the PPD test. A reaction is measured in millimeters of induration (hard swelling) at the site. A PPD skin induration ≥5 mm (or according to local practice/guidelines) is interpreted as a positive result.

6.5.2 Chest X-ray or MRI

A chest X-ray or MRI at Screening (or within 3 months prior to Screening) will be performed to rule out the presence of a pulmonary malignancy of infectious process, in particular tuberculosis.

6.5.3 Physical examination

The physical examination will include the examination of general appearance, skin, neck, eyes, ears, nose, throat, lungs, heart, abdomen, back, lymph nodes, extremities, vascular and neurological system.

Information for all physical examinations must be included in the source documentation at the study site. Significant findings that are present before signing the ICF must be included in the relevant medical history eCRF. Significant findings made after signing the ICF which meet the definition of an SAE must be recorded in the Adverse Event eCRF. All findings meeting the definition of an AE must be recorded from the first administration of study drug on.

6.5.4 Vital signs

This will include blood pressure and pulse rate measurements after 5 minutes rest in sitting position.

If possible, vital signs assessments should be performed by the same study site staff member using the same validated device throughout the study.

6.5.5 Height and weight

Height in centimeters (cm) and body weight (to the nearest 0.1 kilogram (kg) in indoor clothing, but without shoes) will be measured.

If possible, body weight assessments should be performed by the same study site staff member using the same scale throughout the study.

6.5.6 Laboratory evaluations

A central laboratory will be used for analysis of all specimens collected as listed in the sub-sections below (except for urinalysis and ESR). Details on the collections, shipment of samples and reporting of results by the central laboratory are provided to investigators in the laboratory manual. Clinically significant abnormalities must be recorded on the relevant section of the medical history/Current medical conditions/AE CRF page as appropriate. All patients with laboratory tests containing clinically significant abnormal values are to be followed until

Amended Protocol Version v01 Clean

the values return to normal ranges or until a valid reason, other than treatment related AE, is defined.

Clinically notable laboratory results are defined in Appendix 1.

Hematology 6.5.6.1

Hemoglobin, hematocrit, red blood cell count, white blood cell count with differential counts, and platelet count will be measured at scheduled visits.

6.5.6.2 Clinical chemistry

Serum chemistries will include glucose, urea, creatinine, total bilirubin, AST (SGOT), ALT (SGPT), GGT, alkaline phosphatase, sodium, potassium, bicarbonate, calcium, phosphorous, total protein, albumin, and uric acid.

6.5.6.3 Urinalysis

Dipsticks will be provided by the central laboratory to the sites for local urinalysis assessments. The urinalysis results for standard parameters such as protein, glucose, blood and WBCs will be recorded in the appropriate eCRF page.

6.5.7 **Electrocardiogram (ECG)**

A standard 12 lead ECG will be performed as indicated in Table 6-1.

ECGs can be performed externally at a qualified physician but the investigator/qualified site staff must review the tracing. The tracing must then be stored with the subject's source documents. If the ECG findings at screening are clinically relevant and would prevent the subject from participating in the study (taking into account the subject's overall status as well as the medication profile), the subject should be recorded a screen failure and should not receive treatment. Findings at the later ECG readings will be reported as adverse or serious adverse events. If these findings constitute a reason for premature patient withdrawal or would render the overall risk-benefit evaluation of continued participation and treatment in the study unfavorable for the patient, the patient must discontinue study medication.

6.5.8 Pregnancy and assessments of fertility

All pre-menopausal women who are not surgically sterile will have a serum β-hCG test (serum pregnancy test) performed at the second Screening visit and local urine pregnancy tests as indicated in Table 6-1.

A positive urine pregnancy test requires immediate interruption of study drug until serum βhCG is performed and found to be negative.

6.5.9 **Local tolerability (Injection site reactions)**

The local tolerability at the site of s.c. injection of the study treatment will be assessed in case of any local reaction, until this has disappeared.

The assessment of pain, redness, swelling, induration, hemorrhage and itching will be performed by a physician and will be recorded on the Adverse Events eCRF, including the severity (mild, moderate, severe) and the duration.

Tolerability of Secukinumab 6.5.10

Tolerability will be assessed by adverse events, laboratory values and injection site reaction.

6.5.11 Appropriateness of safety measurements

The safety measures used in this study are reliable and relevant standard measures for a biologic in AS. According to local recommendations, a chest X-ray should be performed in clinical practice before initiation of an immunomodulating biologic therapy for AS (DGRh 2009). The radiation exposure that results from the chest X-ray safety measurements at Screening are estimated to be far below 1 mS. For effective radiation doses under 3 mS (300 mrem), the risk is considered to be minimal. Therefore, the radiation exposure in this study involves minimal risk and is necessary to ensure reliable safety measures before the treatment with a biologic.

While hsCRP results are not automatically communicated to the site by the central lab, it will be acceptable to perform a CRP measurement at a local lab in case this is warranted for safety reasons.

The safety assessments selected are standard and adequate for this indication/patient population.

6.6 Other assessments

HLA-B27

6.6.1 HLA-B27

A blood sample to analyze Human Leukocyte Antigen-B27 (HLA-B27) will be obtained from all patients at baseline.

Details on the collection, handling and shipment of the sample to the central laboratory will be provided to investigators in the laboratory manual.

6.6.2 Resource utilization

No measures of Healthcare Resource Utilization (RU) will be collected in the study.

6.6.3 **Pharmacokinetics**

Not applicable.

6.6.4 Other biomarkers

Not applicable.

7 Safety monitoring

7.1 Adverse events

An AE is the appearance or worsening of any undesirable sign, symptom, or medical condition occurring after first intake of study drug even if the event is not considered to be related to study drug. Study drug includes the investigational drugs under evaluation that are given during any period of the study.

Medical conditions/diseases present before first intake of study drug are only considered adverse events if they worsen after study start. Abnormal laboratory values or test results constitute AEs only if they induce clinical signs or symptoms, require dose reduction or temporary or permanent study drug discontinuation or require therapy.

All AEs with a date of onset up to 30 days following after the patient has stopped study participation (defined as time of last dose of study drug taken or last visit whichever is later) must be reported.

The occurrence of AEs should be sought by non-directive questioning of the patient at each visit during the study. AEs may also be detected when they are volunteered by the patient during or between visits or through physical examination, laboratory test, or other assessments. All adverse events must be recorded on the Adverse Events CRF with the following information:

- 1. the severity grade (mild, moderate, severe)
- 2. its relationship to the study drug(s) (suspected/not suspected)
- 3. its duration (start and end dates or if continuing at final exam)
- 4. whether it constitutes a serious adverse event (SAE)

All AEs should be treated appropriately. Treatment may include 1 or more of the following: no action taken (i.e. further observation only); study drug dosage adjusted/temporarily interrupted; study drug permanently discontinued due to this adverse event; concomitant medication given; non-drug therapy given; patient hospitalized/patient's hospitalization prolonged. The action taken to treat the AE should be recorded on the Adverse Event CRF.

Once an adverse event is detected, it should be followed until its resolution or until it is judged to be permanent, and assessment should be made at each visit (or more frequently, if necessary) of any changes in severity, seriousness, the suspected relationship to the study drug, the interventions required to treat it, and the outcome.

The investigator should also instruct each patient to report any new AE (beyond the protocol observation period) that the patient, or the patient's personal physician, believes might reasonably be related to study treatment. This information should be recorded in the investigator's source documents, however, if the AE meets the criteria of an SAE, it must be reported to Novartis.

7.2 Serious adverse events

7.2.1 Definition of SAE

An SAE is defined as any adverse event (appearance of (or worsening of any pre-existing) undesirable sign(s), symptom(s) or medical conditions(s) which meets any 1 of the following criteria:

- is fatal or life-threatening
- results in persistent or significant disability/incapacity
- constitutes a congenital anomaly/birth defect
- requires inpatient hospitalization or prolongation of existing hospitalization, unless hospitalization is for:
 - routine treatment or monitoring of the studied indication, not associated with any deterioration in condition (specify what this includes)
 - elective or pre-planned treatment for a pre-existing condition that is unrelated to the indication under study and has not worsened since signing the informed consent
 - treatment on an emergency outpatient basis for an event not fulfilling any of the definitions of a SAE given above and not resulting in hospital admission
 - social reasons and respite care in the absence of any deterioration in the patient's general condition
- is medically significant, i.e. defined as an event that jeopardizes the patient or may require medical or surgical intervention.

All malignant neoplasms will be assessed as serious under "medically significant" if other seriousness criteria are not met.

Life-threatening in the context of a SAE refers to a reaction in which the patient was at risk of death at the time of the reaction; it does not refer to a reaction that hypothetically might have caused death if more severe (see Annex IV, ICH-E2D Guideline).

Medical and scientific judgment should be exercised in deciding whether other situations should be considered serious reactions, such as important medical events that might not be immediately life threatening or result in death or hospitalization but might jeopardize the patient or might require intervention to prevent 1 of the other outcomes listed above. Examples of such events are intensive treatment in an emergency room or at home for allergic bronchospasm, blood dyscrasias or convulsions that do not result in hospitalization or development of dependency or abuse (see Annex IV, ICH-E2D Guideline).

Any suspected transmission via a medicinal product of an infectious agent is also considered a serious adverse reaction.

All AEs (serious and non-serious) are captured on the CRF, SAEs also require individual reporting to DS&E as per Section 7.2.2.

Information about common side effects already known about the investigational drug can be found in the Investigator Brochure (IB) or will be communicated between IB updates in the form of Investigator Notifications. This information will be included in the patient informed consent and should be discussed with the patient during the study as needed.

7.2.2 SAE reporting

To ensure patient safety, every SAE, regardless of suspected causality, occurring after the patient has provided informed consent and until 30 days after the patient has stopped study participation (defined as time of last dose of study drug taken or last visit whichever is later) must be reported to Novartis within 24 hours of learning of its occurrence.

Any SAEs experienced after this 30 day period should only be reported to Novartis if the investigator suspects a causal relationship to the study drug. For patients who discontinue study medication, SAEs still need to be reported until the end of study, regardless of their suspected relationship to study medication.

Recurrent episodes, complications, or progression of the initial SAE must be reported as follow-up to the original episode, regardless of when the event occurs. This report must be submitted within 24 hours of the investigator receiving the follow-up information. An SAE that is considered completely unrelated to a previously reported one should be reported separately as a new event.

Information about all SAEs is collected and recorded on the Serious Adverse Event Report Form. The investigator must assess the relationship to study drug, complete the SAE Report Form in English, and send the completed, signed form by fax within 24 hours to the German Novartis Clinical Safety & Epidemiology Department. The SAE form should also include information about the concomitant NSAID medication. The telephone and telefax number of the contact persons in the German department of Clinical Safety and Epidemiology, are listed in the investigator folder provided to each site. The original copy of the SAE Report Form and the fax confirmation sheet must be kept with the case report form documentation at the study site.

All SAEs occurring during the follow-up period will be entered in the Adverse Events CRF pages. In addition, an SAE Report Form should be completed. Follow-up information will be sent to the same person to whom the original SAE Report Form was sent, using a new SAE Report Form stating that this is a follow-up to the previously reported SAE and giving the date of the original report. The follow-up information should describe whether the event has resolved or continues, if and how it was treated, whether the blind was broken or not, and whether the patient continued or withdrew from study participation.

Adverse reactions under a Novartis drug of which investigator became aware prior to or during Screening and which were not yet reported should be forwarded to the local Novartis Clinical Safety & Epidemiology Department. This adverse reaction report including the administered Novartis drug and causality assessment should be forwarded independently from the described procedure. Serious adverse reactions occurring under non-Novartis drugs which are not investigational medicinal product (IMP) should be forwarded either to the national competent authority (BfArM or PEI), the Drug Commission of the German Medical Association or the respective marketing authorization holder.

If the SAE is not previously documented in the Investigator's Brochure or Package Insert (new occurrence) and is thought to be related to the Novartis study drug, a Clinical Safety & Epidemiology Department associate may urgently require further information from the investigator for Health Authority reporting. Novartis may need to issue an Investigator Notification (IN) to inform all investigators involved in any study with the same drug that this SAE has been reported.

Suspected Unexpected Serious Adverse Reactions (SUSARs) will be collected and reported to the competent authorities and relevant Ethics Committees in accordance with Directive 2001/20/EC or as per national regulatory requirements in participating countries.

7.3 Liver safety monitoring

Secukinumab has not been studied specifically in patient with hepatic impairments. No pharmacokinetic data are available in these patients. However IgGs are mainly eliminated via catabolism and hepatic impairment is not expected to influence clearance of Secukinumab.

To ensure patient safety and enhance reliability in determining the hepatotoxic potential of an investigational drug, a standardized process for identification, monitoring and evaluation of liver events has to be followed.

The following two categories of abnormalities / adverse events have to be considered during the course of the study:

- Liver laboratory triggers, which will require repeated assessments of the abnormal laboratory parameter
- Liver events, which will require close observation, follow-up monitoring and completion of the standard base liver CRF pages

Please refer to Table 13-1 in Appendix 2 for complete definitions of liver laboratory triggers and liver events.

Every liver laboratory trigger or liver event as defined in Table 13-1 of Appendix 2 should be followed up by the investigator or designated personal at the trial site as summarized below. Detailed information is outlined in Table 13-2 in Appendix 2.

For the liver laboratory trigger:

• Repeating the LFT (Liver Function Test) within the next week to confirm elevation.

Repeat laboratory tests should be entered on the appropriate unscheduled local laboratory CRF page.

• If the elevation is confirmed, close observation of the patient will be initiated, including consideration of treatment interruption if deemed appropriate.

For the liver events:

- Repeating the LFT to confirm elevation as appropriate
- Discontinuation of the investigational drug if appropriate
- Hospitalization of the patient if appropriate
- A causality assessment of the liver event via exclusion of alternative causes (e.g., disease, co-medications)
- An investigation of the liver event which needs to be followed until resolution.

These investigations can include serology tests, imaging and pathology assessments, hepatologist's consultancy, based on investigator's discretion. All follow-up information, and the procedures performed should be recorded on appropriate CRF pages, including the liver event overview eCRF pages.

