5.5.9 Discontinuation of study treatment

Patients may voluntarily discontinue investigational treatment for any reason at any time.

Patients who prematurely discontinue the study should undergo an end of treatment visit (corresponds to the Week 20 visit and also return for the end of study visit at Week 24 (4 weeks after last study treatment (see Table 6-1). The final follow-up visit (Week 24) should be performed before any new treatment is initiated. Study treatment discontinuation must also be recorded in the eCRF and in the IRT.

For patients who are lost to follow-up (i.e., those patients whose status is unclear because they fail to appear for study visits without stating an intention to withdraw from the study), the investigator should show "due diligence" by documenting in the source documents steps taken to contact the patient, e.g., dates of telephone calls, registered letters, etc.

Patients who are prematurely withdrawn from the study will not be replaced.

^{**}See details about corticosteroid management in Section 5.5.7.

Discontinuation of study treatment

Study treatment must be discontinued if the investigator determines that continuation of study treatment would result in a significant safety risk for a patient. The following circumstances **require** study treatment discontinuation:

- Withdrawal of informed consent
- Emergence of the following AEs:
 - Any severe or serious adverse event that is not compatible with administration of study medication, including adverse events that require treatment with an unacceptable concomitant medication
 - Onset of lymphoproliferative disease or any malignancy, except for treated basal cell
 carcinoma, treated actinic keratoses, treated in situ carcinoma of the cervix or noninvasive malignant colon polyps which are being or have been removed
 - Life-threatening infection
 - Any laboratory abnormalities that in the judgment of the investigator are clinically significant and are deemed to place the patient at a safety risk for continuation in the study (A general guidance on clinically notable laboratory values is provided in Appendix 1).
- Pregnancy
- Use of any biologic immunomodulating agent except Secukinumab
- Any protocol deviation that results in a significant risk to the patient's safety

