13.1 Appendix 1: Clinically notable laboratory values and vital signs

The following criteria will be used to define expanded limits and notable abnormalities of key laboratory tests.

Clinically notable values will be forwarded to Novartis/CRO at the same time that they are sent to investigators. Any action based on these laboratory values should be discussed with Novartis/CRO personnel.

Table 13-1 Safety analyses: expanded limits and notable criteria

Amended Protocol Version v01 Clean

		Notable Criteria							
Laboratory Variable		Standard Units	SI Units						
LIVER FUNCTION AND RELATED VARIABLES									
SGOT (AST)		>3 x ULN	>3 x ULN						
SGPT (ALT)		>3 x ULN	>3 x ULN						
Bilirubin		>2 x ULN	>2 x ULN						
Alkaline phosphatase		>2.5 x ULN	>2.5 x ULN						
RENAL FUNCTION, METABOLIC AND ELECTROLYTE VARIABLES									
Creatinine (serum)		>2 x ULN	>2 x ULN						

HEMATOLOGY VARIABLES

Hemoglobin:

20 g/L decrease from baseline

Platelet count:

<100x10E9/L

White blood cell count:

< 0.8 x LLN

Neutrophils:

<0.9 x LLN

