Appendix 2: Liver event and laboratory trigger definitions and 13.2 follow-up requirements

Liver event and laboratory trigger definitions **Table 13-2**

	Definition/ threshold
LIVER LABORATORY	3 x ULN < ALT / AST \leq 5 x ULN
TRIGGERS	$1.5 \times ULN < TBL \le 2 \times ULN$
LIVER EVENTS	ALT or AST > 5 × ULN
	ALP > 2 × ULN (in the absence of known bone pathology)
	TBL > 2 × ULN (in the absence of known Gilbert syndrome)
	ALT or AST > 3 × ULN and INR > 1.5
	Potential Hy's Law cases (defined as ALT or AST > 3 × ULN and TBL > 2 × ULN [mainly conjugated fraction] without notable increase in ALP to > 2 × ULN)
	Any clinical event of jaundice (or equivalent term)
	ALT or AST > 3 × ULN accompanied by (general) malaise, fatigue, abdominal pain, nausea, or vomiting, or rash with eosinophilia Any adverse event potentially indicative of a liver toxicity *
	Any adverse event potentially indicative of a liver toxicity

Table 13-3 Follow-up requirements for liver events and laboratory triggers

Criteria	Actions required	Follow-up monitoring
Potential Hy's Law case ^a	Discontinue the study drug immediately Hospitalize, if clinically appropriate Establish causality Complete liver CRF	ALT, AST, TBL, Alb, PT/INR, ALP and γGT until resolution ^c (frequency at investigator discretion)

Criteria	Actions required	Follow up monitoring
ALT or AST	Actions required	Follow-up monitoring
> 8 × ULN	Discontinue the study drug immediately Hospitalize if clinically appropriate Establish causality Complete liver CRF	ALT, AST, TBL, Alb, PT/INR, ALP and γGT until resolution ^c (frequency at investigator discretion)
> 3 × ULN and INR > 1.5	Discontinue the study drug immediately Hospitalize, if clinically appropriate Establish causality Complete liver CRF	ALT, AST, TBL, Alb, PT/INR, ALP and γGT until resolution ^c (frequency at investigator discretion)
> 5 to ≤ 8 × ULN	Repeat LFT within 48 hours If elevation persists, continue follow-up monitoring If elevation persists for more than 2 weeks , discontinue the study drug Establish causality Complete liver CRF	ALT, AST, TBL, Alb, PT/INR, ALP and γGT until resolution ^c (frequency at investigator discretion)
> 3 × ULN accompanied by symptoms ^b	Discontinue the study drug immediately Hospitalize if clinically appropriate Establish causality Complete liver CRF	ALT, AST, TBL, Alb, PT/INR, ALP and γGT until resolution ^c (frequency at investigator discretion)

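### Section 7.3 leaves stopping study drug to discretion for every liver event, Table 13-3 orders an immediate stop for five of them, and 7.3 cites the wrong table numbers

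*Protocol*

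**What the plan says.** Protocol section 7.3 separates liver laboratory triggers from liver events. Its follow-up list for liver events includes "Discontinuation of the investigational drug if appropriate" and words hospitalization in the same discretionary way. No type of event is excepted.

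For detail, 7.3 gives two pointers. On definitions: "Please refer to Table 13-1 in Appendix 2 for complete definitions of liver laboratory triggers and liver events". On follow-up: "Detailed information is outlined in Table 13-2 in Appendix 2".

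The tables that carry those numbers are:

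- Table 13-1, in Appendix 1: "Table 13-1 Safety analyses: expanded limits and notable criteria". This is the list of notable laboratory values.
- Table 13-2, in Appendix 2: "Liver event and laboratory trigger definitions". It holds definitions and no actions.
- Table 13-3, in Appendix 2: "Table 13-3 Follow-up requirements for liver events and laboratory triggers". Its action column sets out what is required, and several rows begin "Discontinue the study drug immediately".

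Section 5.5.9 lists the circumstances that require study treatment to be discontinued. No liver event is named. The laboratory item reads "Any laboratory abnormalities that in the judgment of the investigator are clinically significant and are deemed to place the patient at a safety risk" and refers to Appendix 1 for guidance; Appendix 2 is not mentioned.

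**The concern.** Section 7.3 asks for one standardized process for liver events, to protect patients and to make the assessment of hepatotoxicity reliable. A site that works from 7.3 has discretion over stopping in cases where Table 13-3 gives none. The numbers in 7.3 do not lead to Table 13-3, and section 5.5.9, where a site would look for mandatory stops, does not lead to Appendix 2 either.

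What is at stake is mainly patient safety. All arms receive injections weekly from Week 0 to Week 8 and again from Week 16 to Week 20 (section 5.2), and home self-injection is allowed from Week 3 (section 5.1.1). A short delay while a site works out which instruction applies can therefore span another injection. A smaller matter is reporting: SAP section 2.8.1 tabulates adverse events leading to discontinuation, and that table would depend in part on which passage a site followed.

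**Working it through.** No arithmetic is needed beyond counting rows, and the documents give no figure to reproduce. The check sets the passages side by side.

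**Step 1. Obligations for the same event.** Table 13-3 has eleven rows. Two cover laboratory triggers (asymptomatic ALT/AST above 3 to 5x ULN, and bilirubin above 1.5 to 2x ULN). That leaves 11 − 2 = 9 rows for liver events.

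| Liver event | Study drug in Table 13-3 | Study drug in section 7.3 |
|---|---|---|
| Potential Hy's Law case | Immediate stop, no condition | Discretionary |
| ALT/AST above 8x ULN | Immediate stop, no condition | Discretionary |
| ALT/AST above 3x ULN with INR above 1.5 | Immediate stop, no condition | Discretionary |
| ALT/AST above 3x ULN with symptoms | Immediate stop, no condition | Discretionary |
| Jaundice | Immediate stop, no condition | Discretionary |
| ALT/AST above 5 to 8x ULN | Stop if elevated for more than 2 weeks | Discretionary |
| Isolated bilirubin above 2x ULN | Immediate stop if elevation persists on repeat | Discretionary |
| Isolated ALP above 2x ULN | No stop instruction | Discretionary |
| Other AE suggesting liver toxicity | Interruption or stop to be considered | Discretionary |

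Count: 5 unconditional + 2 conditional + 1 with no stop + 1 to be considered = 9. The two passages differ in obligation for 5 + 2 = 7 of the 9 rows and are compatible for the other two.

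**Step 2. Hospitalization.** Where Table 13-3 mentions hospitalization it is qualified in every row except jaundice, where it is unqualified. The hospitalization conflict with 7.3 is therefore confined to jaundice.

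**Step 3. Pointers.**

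| Content | Table cited in 7.3 | Where it is |
|---|---|---|
| Definitions | 13-1 | 13-2 |
| Actions | 13-2 | 13-3 |

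Both numbers are one too low. The captions are legible and run in order from 13-1 to 13-4, so this is not an effect of text extraction. Table 13-3 is never cited in 7.3.

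**Step 4. Section 5.5.9.** Take ALT at 9x ULN. Table 13-3 orders an immediate stop. Section 7.3 leaves the stop to discretion. Under 5.5.9 the value would enter through the laboratory item, which turns on the investigator's judgment. Three passages, one event, and only one of them imposes an unconditional duty.

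**The case against.** The strongest reply is that 7.3 describes its list as a summary and sends the reader to Appendix 2, which is the correct appendix and holds both liver tables together. One line in 7.3 has to cover nine kinds of event with different actions, so its discretionary wording can be read as shorthand for whatever the detailed table says. This stands in part: a careful reader will find Table 13-3, and for two rows the wording fits. It does not settle the matter, because nothing in 7.3 says that the table overrides the discretion.

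Four stronger readings are tempting, and the documents do not support them.

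- *Every liver discontinuation becomes an ASAS20 non-responder.* Protocol 9.4.3 and SAP 2.5.3 impute non-response after dropout from the trial, missing data or unblinding. Stopping drug is not on that list. The glossary separates treatment discontinuation from withdrawal, and the primary estimand disregards adherence. A patient may count as a non-responder on leaving the study or lacking Week 12 data, and a stop after Week 12 cannot alter the Week 12 result.
- *With no data monitoring committee, nobody would notice.* Appendix 1 has notable values sent to the sponsor or CRO at the same time as to the investigator, with any action to be discussed. ALT/AST above 3x ULN and bilirubin above 2x ULN are on that list.
- *The ALP limits contradict each other.* Table 13-1 uses 2.5x ULN and Table 13-2 uses 2x ULN, but the tables have different stated purposes and 7.3 names Appendix 2, so the difference alone is not a conflict.
- *Section 5.5.9 permits continued dosing.* Its list is not stated to be exhaustive; sections 5.5.12 and 6.5.7 contain mandatory stops of their own. It also covers severe or serious adverse events incompatible with study medication. What it lacks is a cross-reference.

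**Conclusion.** The point holds as an internal inconsistency. Five liver criteria carry an unconditional immediate stop in Table 13-3 and two more a conditional one, while 7.3 makes stopping discretionary for all of them. Hospitalization conflicts for jaundice only. Both table numbers in 7.3 are wrong, and 5.5.9 gives no route to Appendix 2.

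This rests on reading Table 13-3 as binding, as its caption and action column indicate, and 7.3 as an instruction that sites may act on. The documents give no expected liver event rate for this trial, so the number of patients affected cannot be estimated, and differences between sites are a possibility rather than something shown. No effect on the primary analysis is established. The passages should be reconciled because they concern stopping drug after a serious liver finding and the correction is cheap.

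**What to change.** 1. Reconcile section 7.3 with Table 13-3 so that each liver event has one stated action on study drug and on hospitalization. Which action applies is for the sponsor's safety physicians; this review takes no position on it.
2. Correct the two pointers in 7.3: Table 13-2 for definitions, Table 13-3 for actions.
3. Add a cross-reference to Appendix 2 in section 5.5.9, so that its list and the liver rules agree with what the sponsor confirms.

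The cost is protocol wording and a letter to sites. No new data, procedures or analyses are needed.
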